For the subsequent 30 days, the RAIN exercise will be automatically delivered to the user via the smartphone app prior to each predicted smoking episode according to individual smoking profiles obtained as described below. They will first be asked to rate their craving (“How much are you craving a cigarette?” VAS “very much” to “not at all”) and affect (“How are you feeling?” VAS “very bad” to “very good” ¹⁰⁵). Next, they will be prompted to complete the RAIN exercise, also delivered as a 2-minute audio-guided mindfulness practice with subtitles. After completing RAIN, they will be asked “How helpful did you find this exercise?” (VAS “very helpful” to “not at all”); “How was the timing of this exercise?” (VAS “too early” to “too late”); and to again rate their craving and affect.

D.9. Individualized smoking profiles

Individualized smoking profiles will be obtained using smartband data tracking smoking across the first 21 days of the study, based on the maximum information possible: (1) average times each cigarette is smoked each day; (2) average times each cigarette is smoked on weekdays versus weekends; (3) average time between cigarettes; (4) average wake/sleep time; and (5) average cigarettes per day each day. Less predictable smokers will have less data to inform the prediction algorithm. At the very least, their waking hours will be divided by the number of cigarettes smoked per day and a prompt will be sent at random times in each interval. How much smartband tracking data is needed to adequately develop an individualized smoking profile is a main question in this feasibility trial. We will use this data to then deliver RAIN to the user for 30 days after their quit date. RAIN will be delivered 5 minutes prior to each predicted smoking episode during waking hours.

D.10. Adherence

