intervention: (1) Whether we can accurately detect smoking episodes will be determined by the percent of smoking episodes detected and the rate of false alarms in the first 21 days of the study during which smokers are wearing the smartband to track smoking and upon smoking detection are asked to confirm or deny smoking and self-report any undetected smoking episodes. We expect to replicate previous findings of >80% detection and negligible rate of false alarms [14]. (2) Whether we can deliver mindful smoking triggered by smoking episodes will be determined by the percent of mindful smoking exercises correctly triggered by detected smoking episodes and the rate of false alarms in the next 7 days of the study during which any detected smoking episode triggers a prompt that first asks the smoker to confirm or deny smoking and then launches the mindful smoking exercise. Again, we expect to replicate previous findings of >80% detection and negligible rate of false alarms [14]. (3) Whether we can deliver RAIN to predicted smoking episodes will be measured as average timeliness ratings in the next 30 days of the study during which RAIN is delivered prior to predicted smoking episodes and the smoker is asked to rate whether the exercise was delivered on time. Additionally, we will analyze the craving ratings obtained before participants complete RAIN, as a proxy for whether or not we have targeted moments of high craving. Ratings (Likert items for timeliness, craving) will be evaluated as % of participants and score range (very low, low, moderate, high, very high), with feasibility determined by 75% of participants rating an item (timeliness, craving) as moderate or higher. We expect on average moderate to high timeliness and craving ratings, suggesting that RAIN was delivered in time to help cope with cravings. These and other aspects of treatment fidelity will be reported according to recommended guidelines [17].

Aim 2. To assess adherence to a smartband/smartphone-based brief mindfulness intervention:

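### Aim 1(3) rates RAIN targeting against an absolute 75% threshold, with no predicted-versus-observed comparison and no chance reference

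*Combined protocol and SAP*

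**What the plan says.** Section 13, Aim 1(3), states: "Whether we can deliver RAIN to predicted smoking episodes will be measured as average timeliness ratings in the next 30 days of the study". It adds the craving rating given before each RAIN exercise, "as a proxy for whether or not we have targeted moments of high craving". Success is defined "with feasibility determined by 75% of participants rating an item (timeliness, craving) as moderate or higher", and the expected result is read as "suggesting that RAIN was delivered in time to help cope with cravings".

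Section D.9 builds each profile from the first 21 days of smartband data and then says: "We will use this data to then deliver RAIN to the user for 30 days after their quit date". The lead time is fixed: "RAIN will be delivered 5 minutes prior to each predicted smoking episode during waking hours". For less predictable smokers the minimum rule divides waking hours by cigarettes per day, and "a prompt will be sent at random times in each interval". The same section names the amount of tracking data needed for an adequate profile as a principal question of the trial.

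Aims 1(1) and 1(2) assess detection of smoking and triggering of the mindful smoking exercise. They do not assess prediction.

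**The concern.** The novel technical step in this intervention is predicting when a person would smoke and prompting ahead of that moment. Aim 1(3) is the only part of the analysis that addresses it, and it does so through ratings at the prompts themselves, compared with a fixed level. Nothing shows what those ratings would have been had the prompts fallen elsewhere in the day. A participant whose craving is moderate all day counts as a success wherever the prompts land.

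Two further features weaken the inference. Participants on the random-time fallback are not separated in the analysis, so as written their ratings enter the same summary as those from profile-based prompts. And the question D.9 raises about profile adequacy has no analysis attached.

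At stake is the go-forward decision. A pass could carry prediction-based delivery into the efficacy trial without evidence that it does better than prompts at random times.

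**Working it through.** The plan gives no power, error-rate or precision figure for Aim 1(3), so there is none to reproduce. The checks below show how the 75% rule behaves and what a chance reference would look like.

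**Inputs from the documents.** N=100 for the feasibility trial and a minimum of 5 cigarettes per day (section 6); 12 cigarettes per day in the earlier smartband study (section 13, Aim 2); wear of at least 12 hours a day (D.10); 7 days of mindful smoking before the quit date (D.1).

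**Assumptions not in the documents.** Visual analogue scale 0–100 in five equal bands, so moderate means 40 or more; a participant's value is the mean of about 90 ratings; between- and within-person SD 20; waking day of 12 to 16 hours.

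**Step 1: the craving rule.** The share of participants at moderate or higher is Φ((mean + gain − 40)/√(20² + 20²/90)), where the denominator is 20.1. The rule passes if at least 75 of 100 participants reach that level. Pass probabilities are from simulation.

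| Background mean | Untargeted: share, pass | Gain of 5: share, pass | Gain of 10: share, pass |
|---|---|---|---|
| 40 | 50%, 0% | 60%, 0.1% | 69%, 12% |
| 50 | 69%, 11% | 77%, 75% | 84%, 99% |
| 60 | 84%, 99% | 89%, 100% | 93%, 100% |

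At a mean of 60 the rule cannot tell targeted from untargeted prompts. At 50 it can. At 40 it usually fails even well-targeted prompts. The result is driven by the absolute level of craving, which the plan does not know in advance.

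**Step 2: the timeliness rule.** The item in D.8c runs from too early to too late, so moderate or higher does not mean well timed, and the too-late end would count towards a pass. If ratings were pure noise, uniform on 0–100 (SD 28.9), the mean of k ratings reaches 40 with probability about Φ(10√k/28.9). For k = 10, 30 and 90 this is 86%, 97% and over 99.9%, so the rule passes with probability at least 0.999. With a single rating per participant the share is 60% and the rule passes 0.1% of the time. Section 13 specifies averages.

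**Step 3: chance hit rate for a predicted-versus-observed check.** Take a window of 15 minutes either side, 30 minutes in total. With smoking at random times the chance of a hit is 1 − exp(−CPD × 30/(60H)). With evenly spaced smoking it is CPD × 30/(60H). H is waking hours.

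| Cigarettes/day | Random, 16 h | Random, 12 h | Even, 16 h | Even, 12 h |
|---|---|---|---|---|
| 5 | 14% | 19% | 16% | 21% |
| 12 | 31% | 39% | 38% | 50% |

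The baseline roughly doubles between 5 and 12 cigarettes per day, so it must be set for each participant.

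**Step 4: is the check feasible?** At 12 cigarettes per day, 100 × 12 × 7 = 8,400 predicted episodes. With 84 per person and an assumed ICC of 0.05 to 0.20, the design effect 1 + 83 × ICC is 5.15 to 17.6, and the effective number is 1,631 to 477. For a hit rate near 30%, the 95% half-width 1.96√(0.3 × 0.7/n) is 2.2 to 4.1 points. If only 53 participants contributed (53% completed treatment in the earlier app trial), multiply by √(100/53) = 1.37, giving about 3.0 to 5.6 points.

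**The case against.** A reader might infer that neither measure can ever separate a good profile from chance. The documents do not support that: step 1 shows the craving rule discriminating when background craving is near 50, and the plan gives no background level.

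A reader might also infer that timing ratings are empty because an abstinent participant has no cigarette to time against. Section 13 describes RAIN as help with cravings, and a person can rate timing against an urge. Nor is smoking absent after the quit date. D.1 keeps the band in use and anticipates relapse, so real episodes will be logged.

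It would also go too far to say that craving is never rated away from RAIN prompts. D.5 says ratings after each mindfulness exercise include craving, which would cover mindful smoking, while D.8b lists only helpfulness for that exercise. The two need reconciling.

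Finally, this is a feasibility study whose stated goals are delivery, adherence and acceptability. The plan itself calls craving a proxy and timeliness a user rating. App interactions are time-stamped, so a prediction analysis would remain possible later.

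All of this stands, and it limits the claim. It does not supply the missing comparison. D.9 makes profile adequacy a study question, and choosing window and comparator after seeing the data would weaken the answer.

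**Conclusion.** The concern holds in this form: Aim 1(3) specifies no predicted-versus-observed comparison and no chance reference, so untargeted prompts could meet its criterion, for example when background craving is already moderate or higher. Under the stated assumptions they pass 99% of the time at a background mean of 60 and 11% at 50. These figures rest on assumed scale bands and SDs, and on averaging ratings within participants. The chance hit rates of 14–21% and 31–50% are illustrations of why a baseline is needed. They do not measure error in the planned ratings, because the plan reports no hit rate. The consequence is confined to the conclusion that profile-based delivery works and to what is carried into the efficacy trial. This is a cheap improvement, not a defect that undermines the other feasibility aims.

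**What to change.** Add to Aim 1(3) an offline analysis that leaves delivery unchanged:

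- **Hold-out.** Apply each profile from the first 21 days to the 7-day mindful-smoking week before the quit date. Define that week explicitly, since 21 + 7 = 28 does not reach the day-30 quit date. Report the share of predicted times with a confirmed or self-reported episode within a prespecified window (for example 15 minutes either side, with 5 and 30 minutes as sensitivity analyses), and the time error to the nearest episode.
- **Chance reference.** On the same person-days, compute the same share for times simulated under the D.9 random-in-interval rule. Report the within-participant difference with a 95% CI.
- **Fallback participants.** Report those on the random rule separately. Their difference is about zero by construction.
- **Lapses.** Compare logged post-quit episodes with predicted times, descriptively.
- **Interpretation.** State that post-quit timeliness and craving ratings describe user perception, not prediction accuracy.

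The cost is a modest amount of extra analysis on data already logged. Two limits should be stated: the mindful smoking exercise may shift smoking times in the hold-out week, and pre-quit prediction does not by itself validate craving targeting after the quit date.

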
Aim 1. To determine treatment fidelity for a smartband/smartphone-based mindfulness intervention. Fidelity measures will be: (1) percent of smoking episodes correctly detected and rate of false alarms; (2) percent of "mindful smoking" exercises correctly triggered by smoking and rate

of false alarms; and (3) users' real time ratings of how timely "RAIN" was delivered to predicted smoking episodes, measured as % of participants and score range (very low, low, moderate, high, very high), with feasibility determined by 75% of participants rating timeliness as moderate or higher. We expect to replicate previous findings of >80% detection and negligible false alarms [14] and to find moderate or higher timeliness ratings. These and other aspects of treatment fidelity will be reported according to recommended guidelines [17].

Aim 2. To determine adherence to a smartband/smartphone-based mindfulness intervention.

Adherence measures will be: (1) percent of time spent wearing the smartband; (2) percent of smoking notifications answered; (3) percent of ecological momentary assessment (EMA) ratings (e.g., timeliness, helpfulness, craving, affect) answered; and (4) percent of mindfulness exercises completed. We expect high response rates based on our earlier studies of smartband-based smoking notifications [14] and EMA of craving and other factors [5]. Adherence cut-offs (e.g., time spent wearing the smartband) will be 80%. Adherence was high in pilot work (90% of participants answered 80% of smoking notifications[14]).

Aim 3. To determine the acceptability of a smartband/smartphone-based mindfulness intervention.

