
A.7. The approach in this trial

First, daily smokers will wear a smartband to monitor and detect smoking and will be notified of smoking episodes in real time. As discussed above, smoking can be habitual and “mindless” and self-monitoring of smoking behavior alone may reduce smoking [14]. Next, a “mindful smoking” exercise will be triggered by smoking episodes. Mindful smoking builds on the recognition of one’s smoking behavior enabled by smartband-based monitoring and notification by bringing specific awareness to the present moment effects of smoking –the physical sensations, emotions and thoughts that result from smoking [52, 69]. Through mindful smoking, one gains a clear recognition of the present moment effects of smoking. A clear and nonjudgmental recognition of one’s experience is considered to be a critical step for lasting habit change [69]. A thorough evaluation of the one’s experience of smoking reveals that smoking is not necessarily as gratifying as once perceived, and this begins a process of disenchantment with smoking [52, 70]. Finally, a mindfulness exercise to help cope with cues, cravings and affective states will be delivered to the smoker prior to each predicted smoking episode according to their individualized smoking profile. This exercise teaches smokers how to work mindfully with triggers to smoke using RAIN [52]: Recognize, Allow, Investigate, Note/Not-identify. Smokers learn to (1) Recognize cues, cravings or affective states that trigger smoking; (2) Allow and accept their experience, however pleasant or unpleasant, without trying to change it; (3) Investigate what the experience feels like in the body, emotions and thoughts; and (4) Note/not-identify with what is happening from moment to moment. By openly investigating one’s present moment experiences of craving in a nonjudgmental way, one learns that cravings are physical sensations, thoughts and emotions that will subside. RAIN practice was shown to directly moderate the dissociation of smoking from craving in our in-person trial of mindfulness training [3] and was associated with reduced craving to smoke in our trial of smartphone-based mindfulness training [4, 5]. Overall, this trial tests a three-step intervention in which smokers become aware of their smoking behavior and triggers by tracking

smoking; gain a clear recognition of the actual effects of smoking by mindful smoking; and learn to work mindfully with cravings and triggers rather than smoke using RAIN.

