This study will test the feasibility of a smartband/smartphone-based smoking detection and brief mindfulness intervention (Fig 1), described in detail below. An initial pilot study will be run using the same approach (N=10). First, smokers will wear a smartband for 21 days to automatically monitor and detect smoking and will be notified of smoking episodes in real time to bring attention to their smoking behavior. Their smoking data from this time will be used to develop individualized smoking profiles. They will be instructed to smoke as much or as little as they like [68] but will set a quit date at 30 days. This timing was chosen to balance motivation to quit with time to collect enough smoking tracking data to predict smoking behavior. All subjects will be encouraged at study onset to utilize quit smoking medications to help cope with nicotine withdrawal, to meet clinical guidelines [71] and as in our prior work [72] by directing them to the medications and nicotine replacement therapy pages of <http://smokefree.gov>. Next, they will be provided with information on how mindfulness could be useful to smokers and will be introduced to the brief mindfulness exercises as part of an online mindfulness training (15 min). The “mindful smoking” exercise will then be triggered by any detected smoking episode for 7 days prior to their quit date, to bring awareness to the present moment effects of smoking. Finally, for 30 days post-quit, the RAIN exercise will be delivered to smokers prior to each predicted smoking episode according to their individualized smoking profile, to help them cope with cravings. They will continue to wear the smartband to monitor for smoking, and any detected smoking episode (i.e., relapse) will trigger the mindful smoking exercise. More generally, smokers can “delay” or “skip” any mindfulness exercise and will be compensated for wearing the smartband as described below. Additionally, the mindfulness exercises will be accessible in their previous text messages for the smoker to use any time they have a craving to smoke. All interactions with the smartband app will be time stamped including onset/offset of mindfulness exercises. This trial will test the feasibility of the intervention including treatment fidelity, adherence and acceptability, to inform a larger randomized controlled efficacy trial.

[figure not shown]

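### Section 13 puts pre-RAIN craving under the 75% moderate-or-higher rule, so the criterion leans towards failure when participants do well, and low craving from benefit cannot be told from mistargeted prompts

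*Combined protocol and SAP*

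**What the plan says.** Aim 1, in the opening statement of aims, lists three fidelity measures. The third is participants' real-time rating of how timely RAIN was, "with feasibility determined by 75% of participants rating timeliness as moderate or higher". Craving is not among the three.

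Section 13, Aim 1 (3), goes further. It adds that "we will analyze the craving ratings obtained before participants complete RAIN, as a proxy for whether or not we have targeted moments of high craving", and then sets one rule for both ratings: "with feasibility determined by 75% of participants rating an item (timeliness, craving) as moderate or higher". The expected result is stated as well: "We expect on average moderate to high timeliness and craving ratings, suggesting that RAIN was delivered in time to help cope with cravings".

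D.4 and the overview of Section 13 state the 75% rule for rating items in general, with timeliness as the example. Only Aim 1 (3) in Section 13 names craving.

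On timing, D.8(c) says of each RAIN prompt: "They will first be asked to rate their craving". The answer is given on a visual analogue scale before the exercise starts. D.9 builds the smoking profile from the first 21 days and continues: "We will use this data to then deliver RAIN to the user for 30 days after their quit date".

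On what may move craving, A.7 reports that RAIN practice "was associated with reduced craving to smoke in our trial of smartphone-based mindfulness training", and D.1 says: "All subjects will be encouraged at study onset to utilize quit smoking medications to help cope with nicotine withdrawal". A.5 adds that such medications lower background craving but do not relieve craving set off by cues, thoughts or affect. Section 6 names medication use as a possible confounder to be monitored.

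**The concern.** The rule treats a high level of craving as evidence that prompts arrived at the right moments. But the level of craving after a quit date does not depend on prompt timing alone. It also depends on how well the participant is doing: practice effects carried over from earlier RAIN sessions, time since the last cigarette, and medication. A participant whose craving has faded counts against feasibility even if every prompt fell exactly where a cigarette used to be. A participant who craves all day counts in favour, however poorly the prompts are placed.

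At stake is how one stated pass/fail item is read. D.1 says that the trial is to inform a larger randomised efficacy trial. A missed craving criterion could be taken to mean that the profile-based prompts do not work, when part of the explanation may be that participants improved.

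**Working it through.** There is no figure in the plan to reproduce. The 75% is a chosen cut-off. The documents give no expected share, standard deviation, error rate or power for this criterion.

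**Step 1. What a low pre-RAIN rating can mean under the plan.**

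| Reason for low craving at the prompt | Prompt well placed? | Effect on the criterion |
|---|---|---|
| Prompt away from the usual smoking time | No | Lowers the share |
| Carry-over from earlier RAIN practice (A.7) | May be | Lowers the share |
| Medication lowering background craving (A.5, D.1) | May be | Lowers the share |
| Craving fading with abstinence | May be | Lowers the share |

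All four rows look the same in the analysis. D.8 asks for momentary craving only immediately before and after RAIN, so there is no rating from unprompted moments to compare with. The criterion carries no stratification or adjustment for medication, smoking status or time since quitting.

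**Step 2. How sharply the rule reacts to the true share.** Let p be the true share of participants at moderate or higher (assumed values) and n the number with ratings. Then P(meet the cut) = P(X ≥ ⌈0.75n⌉), with X ~ Binomial(n, p). The values of n are 100 (feasibility sample, Section 6), and 84 and 53. The last two apply to 100 participants the 84% survey retention and 53% treatment completion that Section 13 reports for the earlier app trial.

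| p | n = 100 (75 or more) | n = 84 (63 or more) | n = 53 (40 or more) |
|---|---|---|---|
| 0.85 | 0.997 | 0.995 | 0.978 |
| 0.80 | 0.913 | 0.898 | 0.841 |
| 0.75 | 0.553 | 0.558 | 0.542 |
| 0.70 | 0.163 | 0.190 | 0.239 |
| 0.65 | 0.021 | 0.033 | 0.070 |

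**Step 3. How large a fall in craving brings the share to 75%.** Assume that person-level craving is normal and shifts down by d standard deviations with prompt timing unchanged. The share becomes Φ(z(base) − d), so the shift that reaches 75% is d = z(base) − z(0.75):

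- from 0.80: 0.17 SD
- from 0.85: 0.36 SD
- from 0.90: 0.61 SD
- from 0.95: 0.97 SD

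From a base of 0.85 with n = 100, a fall of 0.2 SD gives a share of 0.799 and a 0.906 chance of meeting the cut. A fall of 0.5 SD gives 0.704 and 0.186.

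**Step 4. If only some participants improve.** Let a fraction m have a lowered chance of being at moderate or higher: p = base × (1 − m) + low × m. The share reaches 75% at m = (base − 0.75)/(base − low). Base is 0.85 and n = 100.

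- low = 0.50: crossing at 0.10/0.35 = 28.6% of participants. At m = 25%, p = 0.762 and the chance is 0.67. At m = 50%, p = 0.675 and the chance is 0.065.
- low = 0.70: crossing at 0.10/0.15 = 66.7%. At m = 25%, the chance is 0.954.

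So a modest fall in craving may still pass and a larger one will probably not. In every scenario the chance moves down as craving falls.

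**The case against.** The strongest defence is that this is a fidelity measure, not an efficacy measure. If craving is low at the prompt for any reason, the prompt did not reach a moment of high craving. Whether a profile built before quitting still finds such moments afterwards is a fair feasibility question. That justifies collecting and analysing the rating. It does not justify a pass mark on its absolute level, because that level cannot show whether the prompt was misplaced or the craving had gone.

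A reader might infer that an intervention or medication that lowers craving would necessarily fail the fidelity test. The documents do not support that:

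- Failure needs more than 25% of participants below moderate, and neither a baseline level nor an effect size is given.
- A.5 says that cravings may go on arising, reports similar craving levels in the two arms of the earlier trials, and expects the link between craving and smoking to weaken rather than the level itself. It also limits the medication effect to background craving.
- The rating comes before RAIN, so the immediate fall within a session does not count. Only carry-over, abstinence and background effects do.

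These points limit the size but do not remove the bias. Similar levels between arms do not show that craving stays at moderate or higher over 30 days after quitting. The question put to participants does not separate background from cue-induced craving.

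Two further inferences also go too far. One is that the two statements of Aim 1 contradict each other outright. Section 13 presents craving as an addition, and the general rule in D.4 is wide enough to cover it, so the wording needs reconciling. The other is that missing this item fails Aim 1. No section says so; craving sits beside detection, triggering and timeliness.

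**Conclusion.** The point holds as a bias, not as a certainty. As written, the 75% rule on pre-RAIN craving is more likely to be missed the better participants do after quitting, and the plan cannot distinguish that from mistargeted prompts. The opening statement of Aim 1 does not ask for this criterion.

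Its size cannot be fixed from the documents. The binomial figures rest on assumed true shares and on one independent classification per participant. The shift calculation also assumes normality. The plan does not say how the analogue scale maps to the five categories, or how a participant's repeated ratings over 30 days become one classification, and either choice would move the results. The practical consequence is confined to one supporting item in a feasibility trial, but that item is a stated pass/fail rule and is easily corrected before analysis.

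**What to change.** In Section 13, Aim 1 (3), remove craving from the 75% rule so that it covers timeliness only, as in the opening statement of Aim 1. Keep pre-RAIN craving as a descriptive targeting proxy, reported by week since the quit date, by smoking status and by medication use, with the category cut-points and the per-participant summary defined in advance. Replace the sentence on expected results so that moderate-to-high craving is no longer presented as evidence of success on its own.

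Do not use a comparison of profile-based prompts with the random-time fallback prompts as a targeting check. D.9 gives the fallback to smokers whose pattern is harder to predict, so the comparison would be between different people.

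The cost is a change of wording. App interactions are already time stamped (D.1), and smoking status and medication use are already collected at each survey (Table 1). The downside is that one supporting pass/fail item becomes descriptive.
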